16.4.3. ANALYSIS OF ADDITIONAL EFFICACY ENDPOINT

The number and percentage of patients alive and dead through Day 60 (refer to Section 16.4.1.1) along with the two-sided 95% CI for the percentage of patients dead through Day 60 will be provided by treatment arm. Primary reason of death will also be summarized by treatment arm. No statistical inference will be performed for this endpoint but treatment effect estimate (i.e., relative risk, odds ratio) and two-sided 95% CI will be provided.

16.4.4. SENSITIVITY ANALYSES FOR ADDITIONAL EFFICACY ENDPOINT

No sensitivity analyses will be performed for the additional efficacy endpoint.

CCI [Redacted]

PPD [Redacted]

Version Number: Amendment 1, v1.0
Version Date: 23Apr2021

CCI [Redacted]

[figure not shown]
[Redacted]

[Redacted]

[Redacted]

[Redacted]

[Redacted]

16.4.5. SUPPLEMENTARY ANALYSES FOR ADDITIONAL EFFICACY ENDPOINT

The time to all-cause death through Day 60, in days, will be derived as follows:

- Time to all-cause mortality through Day 60 (days) =
(Date of death / Date of censoring - Date of Study Day 1 [refer to Section 6.1]) + 1.

The date of death will be taken from data captured on the *Death Details* page of the eCRF.

For patients who were alive or patients with an unknown alive status at the time of the analysis due to missing data, time to all-cause mortality will be censored at the latest date on which the patient was known to be alive before or on Day 60. The last date the patient was known to be alive will be the latest date collected on any page of the eCRF.

For patients who discontinued from the study before Day 60, time to all-cause mortality will be censored at the date of study discontinuation, as captured on the *Disposition* page of the eCRF.

Number and percentage of patients with and without the event will be presented by randomized treatment arm. For patients who did not meet the event, the main reason for censoring (refer to Section 16.1.1) will be summarized similarly.

The incidence of all-cause mortality through Day 60 along with its two-sided 95% CI by treatment arm will then be estimated using Kaplan-Meier survival curves of the time to all-cause mortality through Day 60. Kaplan-Meier survival curves by treatment arm will also be provided.

The 25th percentile, 50th percentile (median), and 75th percentile of time to all-cause mortality (days) with the corresponding two-sided 95% CIs based on the Kaplan-Meier survival curves for each treatment arm will be presented. The estimate of the SEs will be computed using Greenwood's formula, the CI for the median will be calculated according to Brookmeyer and Crowley (1982) and the CIs for the survival function estimates at above mentioned time points will be derived from the Kaplan-Meier estimates using the log-log transformation.

Finally, a Cox proportional hazard model will be performed, including the baseline clinical severity of 2 on the 8-point ordinal scale for clinical severity (yes or no), remdesivir use at baseline (yes or no) stratification variables, both as captured on the IWRS, country (region), and treatment arm as factors. Ties will be handled using the exact method. The hazard ratio of the candidate agent plus SoC vs. placebo plus SoC and its associated two-sided 95% CI will be provided.

16.5. INTERIM ANALYSIS

16.5.1. INTERIM ANALYSIS FOR FUTILITY

Each candidate agent may be evaluated for futility at up to two IAs.

The IAs will be based on analyses of the primary efficacy endpoint (refer to Section 16.1.1), using the analysis methods described in Section 16.1.3.

The IAs are planned at information fractions of approximately 25% and 55% of expected number of confirmed clinical recoveries (refer to Table 1), i.e., after approximately 123 and 270 patients have met the primary endpoint of confirmed clinical recovery on a particular candidate agent plus SoC and its contemporaneous placebo plus SoC, respectively. However, the timing of these IAs may be adjusted due to operational considerations, e.g., actual enrollment rate.

For the IAs, a Pocock beta spending function will be used for non-binding futility boundary specification. This strategy will allow for ineffective agents to be identified early for discontinuation of further evaluation. Assuming no treatment effect for a candidate agent plus SoC arm compared with placebo plus SoC patients included in the control arm of the candidate agent, there is a 49.7% chance that enrolment to this agent is stopped at the first IA and 34.6% chance at the second IA. Under the scenario that treatment has a negative effect on outcome (refer to Table 2), these probabilities become 72.3% and 24.7%, respectively.

The primary analysis for a candidate agent will occur after 350 patients have been randomized to a particular candidate agent plus SoC and have had the opportunity to complete the Day 29 visit, when approximately 490 confirmed clinical recovery events are expected to have been observed in total across the candidate plus SoC arm and placebo plus SoC patients included in the control arm of the candidate agent, unless a candidate agent is stopped early for futility. The final analysis of a candidate agent will occur after all patients randomized to that candidate agent plus SoC and the concurrent placebo plus SoC controls have had the opportunity to complete the Day 60 visit.

Table 1 and Table 2 present a summary of futility incremental probabilities at the first interim and second interim analyses together with Pocock futility boundaries in the scenario of 88.3% estimated power when the IAs occur at information fraction of 25% and 55% of expected number of recoveries, respectively.

CCI

PPD

Version Number: Amendment 1, v1.0
Version Date: 23Apr2021

CCI

Table 1 Summary of Futility Probabilities and Boundaries with 88.3% Power using Pocock Futility Boundaries

Analysis	Total Number of Events (Information Fraction)	Boundary of Futility, Non-binding (HR)	Boundary of Futility, Non-binding (p-value)	Incremental Probability to Declare Futility under the Null (HR=1)
First Interim	123 (25%)	≤ 0.998	0.503	0.497
Second Interim	270 (55%)	≤ 1.121	0.175	0.346

HR=hazard ratio.

Assume 1-sided α of 0.025.

Interim analyses using Pocock futility boundaries at 25% and 55% information fraction.

HR boundaries are translated from p-values, dependent of relative timing, and will be re-calculated for IDMC.

Table 2 Summary of Futility Probabilities and Boundaries with 88.3% Power using Pocock Futility Boundaries for the Negative Treatment Scenario (HR=0.9)

Analysis	Total Number of Events (Information Fraction)	Boundary of Futility, Non-binding (HR)	Boundary of Futility, Non-binding (p-value)	Incremental Probability to Declare Futility under the Negative Treatment Effect Scenario (HR=0.9)
First Interim	123 (25%)	≤ 0.998	0.503	0.723
Second Interim	270 (55%)	≤ 1.121	0.175	0.247

HR=hazard ratio.

Assume 1-sided α of 0.025.

Interim analyses using Pocock futility boundaries at 25% and 55% information fraction.

HR boundaries are translated from p-values, dependent of relative timing, and will be re-calculated for IDMC.

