### **6.3 Measures to Minimize Bias: Randomization and Blinding**

The study will randomize patients on an ongoing basis, in a double-blind manner, to receive either one of the active candidate agents plus SoC or to receive placebo plus SoC. Randomization will be performed using an Interactive Voice/Web Response System (IVRS/IWRS). The system will initially randomize to either an active candidate agent or generically to placebo plus SoC. If a patient is randomized to placebo plus SoC, the system will then further randomize the patient to a specific candidate agent's placebo from within the list of candidate agents available at the site and for which the patient was determined to be eligible. In either of these cases, the blinded team will be aware of the sub-protocol to which the patient has been randomized, but not whether it is the active agent or the agent's matching placebo. The system will limit randomization to those agents (or matching placebo) that are active for randomization, have not reached their total number of planned patients, have been approved by the site, and for which the patient matches the inclusion/exclusion criteria.

If candidate agents are added to and/or dropped from the study, randomization will proceed with an equal probability of assignment to each of the remaining candidate agents, except for situations where a patient does not meet the eligibility criteria for, and hence would be excluded from, one or more of the sub-protocols.

Study treatment will be dispensed at randomization or according to the sub-protocol SoA. Returned study treatment should not be re-dispensed to patients.

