The primary analysis for a candidate agent will occur after 350 patients have been randomized to an active agent plus SoC and have had the opportunity to complete the Day 29 visit, when approximately 490 clinical recovery events are expected to have been observed, unless an agent is stopped early for futility. The final analysis for a candidate agent will occur after all patients randomized to that agent plus SoC and the concurrent placebo plus SoC controls have had the opportunity to complete the Day 60 visit.

[Appendix 7](#) presents a summary of futility incremental probabilities at the first interim, second interim, and the primary analyses together with Pocock futility boundaries in the scenario of 88.3% estimated power when the analyses occur at information fractions of 25% and 55% of expected number of recoveries, respectively.

Details will be provided in the IDMC charter and SAP.

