4.3. PRIMARY ANALYSIS

The primary analysis for a candidate agent will take place after:

- Approximately 350 patients have been randomized to the candidate agent plus SoC active arm of the sub-protocol of interest and approximately 350 patients have been randomized to the shared placebo plus SoC control arm of the sub-protocol of interest (refer to Section 4.5), and last patient randomized into one of these two arms is from the sub-protocol of interest, because if the last randomized patient is from a sub-protocol other than the one of interest, the patient’s treatment arm will automatically be unblinded since those patients can only be included in the shared placebo plus SoC control arm of the sub-protocol of interest;
- The last patient randomized to that candidate agent plus SoC treatment arm or its concurrent shared placebo plus SoC control arm have had the opportunity to complete the Day 29 study visit or discontinued from study before or on the Day 29 study visit;
- Sponsor authorization of this SAP;
- Sponsor authorization of the analysis sets (refer to Section 5.3);
- Interim or final database lock of each sub-protocol contributing to the shared control group of the candidate agent, as applicable;
- Interim database lock of the concerned candidate agent database (refer to DM Interim Database Lock Plan).

The data cut-off date will be the date the last patient completed the Day 29 study visit or discontinued from the study before or on the Day 29 study visit, whichever occurs first.

With the following exception, all planned analyses identified in this SAP will be performed by CCI Biostatistics at the time of the primary analysis of a sub-protocol. The exception is the summary and analysis of the secondary efficacy endpoint incidence of sustained clinical recovery as confirmed by Day 60 (refer to Section 16.2.1.9) which will be performed at the time of the final analysis of a sub-protocol (refer to Section 4.4).

For each sub-protocol, additional outputs to be produced at the time of the primary analysis may be specified in sub-protocol SAPs.

CCI [Redacted]

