4.5. SELECTION OF THE CONTROL ARM FOR AN ANALYSIS

The subset of the placebo plus SoC group, regardless of which sub-protocol the placebo patient belongs, enrolled concurrently to an active agent with matching inclusion/exclusion criteria will serve as the control arm for the analysis of a candidate agent. An exception to this definition is that if a sub-protocol X is not open at a site for screening, the concurrent placebo from other active sub-protocol(s) at that site will not be eligible for inclusion in the control arm for sub-protocol X. This is because patient’s eligibility for sub-protocol X cannot be determined without sub-protocol consent and obtaining consent for a sub-protocol is not possible until that sub-protocol is opened at a site for screening. It is to be noted that a patient randomized to the placebo arm of sub-protocol X taking the candidate agent of sub-protocol Y for another approved indication (based on data collected on the *Concomitant Medications* page of the eCRF) at the time of randomization will not be eligible for the control arm of the sub-protocol Y.

For each sub-protocol and each site, ‘concurrently’ is defined as the period starting on the date the site was opened

CCI [Redacted]	[Redacted]	Version Number:	Amendment 1, v1.0
PPD [Redacted]	[Redacted]	Version Date:	23Apr2021
CCI [Redacted]	[Redacted]	[Redacted]	[Redacted]
[Redacted]	[Redacted]	[Redacted]	[Redacted]
[Redacted]	[Redacted]	[Redacted]	[Redacted]

for screening for the sub-protocol and ending on the date of the last patient randomized into that sub-protocol for an interim, primary, and final analyses. For IDMC safety analyses, the date of the data cut-off will be used in lieu of the date of the last patient randomized into the sub-protocol.

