7.1. SAMPLE SIZE CALCULATION

A total of up to 350 patients are planned to be randomized to each candidate agent plus SoC. Simultaneously, patients will be randomized to placebo plus SoC throughout the course of the study. The subset of shared placebo

CCI

PPD

Version Number: Amendment 1, v1.0
Version Date: 23Apr2021

CCI

plus SoC treatment arm, regardless of which sub-protocol the placebo belongs, enrolled concurrently to an active agent with matching inclusion/exclusion criteria will serve as comparator (refer to Section 4.5). The primary efficacy endpoint to compare selected treatment plus SoC to placebo plus SoC included in the control arm will be the time to confirmed clinical recovery through Day 29 i.e., fit for discharged (defined by achieving a score of 6, 7 or 8 on the 8-point ordinal scale for clinical severity status), without re-hospitalization through Day 29 (refer to Section 16.1.1).

Assuming a median time to confirmed clinical recovery of 11 days for patients randomized to a candidate agent plus SoC arm compared with 15 days for those randomized to its concurrent placebo plus SoC arm, 350 patients are needed per arm in order to observe 490 confirmed clinical recovery events between the 2 treatment arms being compared at the primary analysis of a sub-protocol. This sample size will provide approximately 88% power to detect a hazard ratio (HR) of 1.364 for the occurrence of the confirmed clinical recovery events, when comparing each candidate agent plus SoC with their concurrent placebo plus SoC arm, at a one-sided significance level of 0.025.

This sample size will provide the following information about the key secondary efficacy endpoints:

- Assuming the oxygen-free recovery rate at Day 29 is 65% for the concurrent placebo plus SoC arm of a candidate agent, a sample size of 350 patients per arm will provide approximately 80% power to detect a 9.7% absolute increase in the proportion of patients who have oxygen-free recovery at Day 29 in the candidate agent plus SoC arm;
- Assuming 70% of patients randomized to the concurrent placebo plus SoC arm of a candidate agent achieve at least 2-point improvement from baseline on the 8-point ordinal scale or are fit for discharge at Day 29, 350 patients per arm will provide approximately 80% power to detect a 9.2% absolute increase in this proportion with a candidate agent plus SoC arm at Day 29;

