4.5.2. FINAL ANALYSIS

For final analysis of this sub-protocol, the control arm (also referred to as shared placebo + SoC arm) will include all patients randomized to the placebo arm of any sub-protocol before this sub-protocol was early terminated (refer to section 3.3) at a site at which:

- This sub-protocol was opened for enrollment.
- At least one patient was randomized to either this sub-protocol active (Lanadelumab- intra-venous [IV] + SoC) or placebo (placebo to Lanadelumab-IV + SoC) arms.

That is, patients that satisfy these criteria will be included in the control arm of this sub-protocol regardless of 1) whether patients was randomized before this sub-protocol was opened for enrollment at the site (that is, patients randomized after enrollment into COV-01-001 sub-protocol was early terminated will be excluded from the control

arm of this sub-protocol) and 2) patient’s eligibility to this sub-protocol specific inclusion/ exclusion criteria.

The purpose of this change from the Master SAP control arm definition (Master SAP Section 4.5) is to minimize the randomization imbalance issue noted by the CCI Unblinded Biostatistician and IDMC members at the time of CCI. At the time this sub-protocol SAP was finalized, the randomization imbalance was estimated to be approximately 7:1 between this sub-protocol active and control arms, should the original control arm definition would have been retained for the final analysis of this sub-protocol.

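### The primary-analysis trigger counts only the active arm in SAP 16.5.1 and Protocol 9.1 but both arms in SAP 4.3, and the stated 88% power holds only with about 350 patients in each

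*SAP*

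**What the plan says.** Four places give an active-only trigger. SAP 16.5.1: "The primary analysis for a candidate agent will occur after 350 patients have been randomized to a particular candidate agent plus SoC". Protocol 9.1: "The primary analysis for a candidate agent will occur after 350 patients have been randomized to an active agent plus SoC". The Figure 1 notes in Protocol 1.2 and SAP 3.1 agree. In Protocol 9.1 and SAP 16.5.1 the 490 recovery events are an expectation at that time, not a condition, and no minimum control count is set.

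Two places count both arms. SAP 4.3, which governs the primary analysis, requires about 350 active patients and also that "approximately 350 patients have been randomized to the shared placebo plus SoC control arm of the sub-protocol of interest". SAP 4.4 repeats this for the final analysis.

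The power statement in SAP 7.1 is built on 350 patients per arm: "This sample size will provide approximately 88% power to detect a hazard ratio (HR) of 1.364", "at a one-sided significance level of 0.025".

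Three other provisions bear on whether the control count can be reached:
- Protocol 6.3 limits randomization to agents that "have not reached their total number of planned patients".
- Master SAP 4.5 defines the concurrent control period at each site as "ending on the date of the last patient randomized into that sub-protocol for an interim, primary, and final analyses".
- The COV-01-001 SAP (4.5.2) reports that, under the Master SAP control definition, "the randomization imbalance was estimated to be approximately 7:1 between this sub-protocol active and control arms". The COV-01-005 SAP (4.5.2) gives the same estimate. Both SAPs replace the definition for their final analysis.

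The COV-01-004 SAP states no change to planned analyses (3.3) and takes its sample size from the Master SAP (7.1).

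**The concern.** The two rules describe the same moment only if active and shared-control patients accrue at 1:1. If the control arm lags, a team following SAP 16.5.1 or the protocol would run the confirmatory analysis with fewer controls than the power calculation assumes, while a team following SAP 4.3 would wait. Nothing says which rule governs, or what happens if controls are short when the active arm is full.

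Two sub-protocols departed from 1:1 by a wide margin on their own SAPs' estimates, so this is not a remote case. What is at stake is the meaning of a non-significant result, which could be read against a power the comparison did not have. There would also be a choice of trigger or control pool, made late, that ought to have been settled in advance.

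**Working it through.** **Inputs.** HR 1.364 (15/11, from medians of 15 and 11 days), one-sided 0.025, 350 per arm and 490 events (SAP 7.1). Futility looks at about 123 and 270 events, with p-value boundaries 0.503 and 0.175 (SAP 16.5.1, Table 1), which are z = -0.0075 and 0.9346.

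**Formula.** With D events and active share p, the information is I = D·p·(1-p). Power without looks is Φ(√I·ln HR - 1.96). With looks, Z1, Z2 and Z3 are jointly normal with means √I_k·ln HR and correlations √(I_j/I_k), and power is P(Z1 > -0.0075, Z2 > 0.9346, Z3 > 1.96).

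**Reproducing the plan.** At 1:1, I = 490 × 0.25 = 122.5 and √122.5 × ln 1.364 = 3.436, so power without looks is Φ(1.476) = 93.0%. With the looks it is 88.3%, the plan's figure. Under HR = 1 the model gives stopping probabilities 0.497 and 0.346, as in Table 1.

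**Active-only trigger met with fewer controls.** The active arm is 350. The plan states no event rate, so two assumptions are shown: a flat 70% (490/700), and exponential times from the stated medians over 29 days (83.9% active, 73.8% control). The looks are placed either at 25% and 55% of the events actually reached, or at the planned 123 and 270 events.

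| Active:control | Controls | Events, 70% | I, 70% | No looks, 70% | Looks 25/55%, 70% | Looks 123/270, 70% | Looks 25/55%, exponential | Looks 123/270, exponential |
|---|---|---|---|---|---|---|---|---|
| 1:1 | 350 | 490 | 122.5 | 93% | 88% | 88% | 91% | 90% |
| 1.5:1 | 233 | 408 | 98.0 | 87% | 81% | 84% | 86% | 86% |
| 2:1 | 175 | 368 | 81.7 | 80% | 74% | 78% | 79% | 82% |
| 3:1 | 117 | 327 | 61.3 | 68% | 61% | 67% | 68% | 72% |
| 7:1 | 50 | 280 | 30.6 | 40% | 35% | 40% | 41% | 45% |

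Worked line for 7:1: D = 0.7 × 400 = 280; I = 280 × 0.875 × 0.125 = 30.6, which is 25% of 122.5; √30.6 × ln 1.364 = 1.718; Φ(1.718 - 1.96) = 40% without looks. The information at 2:1 and 3:1 is 67% and 50% of plan.

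**Two further checks.** Reaching 490 events is not enough if the arms are unbalanced: at 7:1 with 490 events, I = 53.6 and power is 62% without looks and 56% with them. With 350 active patients and a 70% event rate, about 345 controls are needed to keep 88% with the looks at 25% and 55%, so on that basis the stated figure leaves almost no room for a control shortfall.

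**The case against.** The best defence is that SAP 4.3 is the operative section, already requires about 350 controls, and is repeated in 4.4. The sentence in 16.5.1 sits in the futility section and expects 490 events across both arms, and SAP 7.1 ties 88% to 350 per arm. On that reading the power claim is conditional and the defect is a wording mismatch. This largely stands. If about 350 controls are reached, power is 88.3%. What it leaves open is which rule governs and what happens when the control count is short.

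Several stronger readings are tempting, and the documents do not support them:
- **That COV-01-004 ran at 7:1 or was underpowered.** No ratio is given for it. The 7:1 figures are estimates from sub-protocols stopped after 29 and 108 randomized patients, neither of which will have an interim or primary analysis.
- **That 1:1 was kept for COV-01-004 in the knowledge of 7:1.** The Master and COV-01-004 SAPs are dated 23 April 2021. The SAPs reporting 7:1 are dated 23 and 28 July 2021.
- **That the SAP 4.3 condition can never be met once controls lag.** Protocol 6.3 does not say whether the planned total means the active arm or active plus placebo, and the SAP 4.5 window runs to the last patient randomized into the sub-protocol, which includes its own placebo arm. The documents support only that no step is stated.
- **That the imbalance can be tested against chance.** The arm splits are not given, and 29 and 108 count patients randomized into the sub-protocol, not active plus shared control.

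It is also fair to say that the futility boundaries are non-binding and that the planned hazard ratio with its 95% confidence interval will show the precision achieved. That helps interpretation but does not settle when to analyse.

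**Conclusion.** The trigger is stated inconsistently: active-only in SAP 16.5.1, Protocol 9.1 and both Figure 1 notes, two-arm in SAP 4.3 and 4.4. The 88% belongs to the two-arm condition. If the active-only rule were followed with 350 active patients, power would be about 81-86% at 1.5:1, 74-82% at 2:1, 61-72% at 3:1 and 35-45% at 7:1. The low ends use a 70% event rate with looks at 25% and 55% of the reduced events; the high ends use exponential event rates with looks at 123 and 270 events. All assume HR 1.364 and that the futility boundaries are followed. The 7:1 line illustrates what two stopped sub-protocols estimated and is not a forecast. The consequence concerns agents still under the Master SAP rules, such as COV-01-004.

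**What to change.** 1. In SAP 16.5.1, the Figure 1 notes in Protocol 1.2 and SAP 3.1, and Protocol 9.1, replace the active-only trigger with the SAP 4.3 condition: about 350 active and about 350 shared-control patients, all with the opportunity to complete Day 29. Have the unblinded statistician monitor the control count, since SAP 4.2 passes only overall counts to the blinded statistician.
2. In Master SAP 7.1, state that 88% applies only at about 350 per arm. Add that, if controls are short when enrolment closes, power will be restated for the realized allocation and number of events at the design hazard ratio.

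A trigger on information alone (I = 122.5) is not a good substitute. It needs 122.5/(2/9) = 551 events at 2:1 and 122.5/0.109375 = 1,120 at 7:1, against about 368 and 280 available from 350 active patients at a 70% event rate. It would also drop the per-arm patient counts on which the key secondary power statements rest.

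The cost is SAP and protocol wording and a power figure that may be less favourable. The restatement needs no added patients.
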